14.1 BIOSTATISTICS

This phase II trial will explore the efficacy of treating high-risk MDS and AML patients with 5'-azacitidine following TCD-HSCT. Based on historical MSKCC data for patients with advanced MDS and AML (adults and pediatrics) with high relapse risk, who meet the entry criteria, the two-year

cumulative incidence of relapse is 35%. Therefore, this intervention would be considered promising if the two-year relapse proportion is 15% or less. If the relapse proportion is 35% or greater, the 5-azacitidine intervention would not be considered promising. Therefore, using a single stage exact design, a total of 32 patients will accrue on study. At the end of the trial, if seven or fewer patients relapse by two years post treatment initiation, the trial will be considered promising. If, however, more than 8 patients relapse at any point the study will be considered unpromising and will be closed for further accrual. The type I and type II errors for this trial are 0.08 and 0.10, respectively. It is anticipated that enrollment will be completed in 5 years with an accrual of approximately 6-7 patients/year.

If a patient is found to be ineligible for reasons unrelated to disease relapse or progression, or is lost to follow-up, s/he will be replaced for the primary endpoint. If a patient dies for reasons unrelated to disease relapse or progression (i.e., treatment related mortality), s/he will remain as part of the 32 patient cohort. Treatment-related mortality will be monitored as part of the stopping rules discussed below.

In order to reduce patient risk and confirm the safety of 5'-azacitidine in this setting, the study design includes early termination in event of severe neutropenia, severe thrombocytopenia, and treatment-related mortality. The boundaries are based on accrual of 32 patients. The calculations in the table below are based on marginal probabilities.

Failure Type	# of failures needed to stop the study	Failure rate in the population	Probability boundary is crossed
Neutropenia (Grade III-IV)	3 in the first 8 patients 4 in the first 14 patients 5 in the first 20 patients 6 in the first 27 patients 7 at any point	0.1	0.1
		0.3	0.92
Thrombocytopenia (Grade III-IV)	3 in the first 8 patients 4 in the first 14 patients 5 in the first 20 patients 6 in the first 27 patients 7 at any point	0.1	0.1
		0.3	0.92
	3 in the first 5 patients 4 in the first 8 patients 5 in the first 12 patients	0.15	0.07

Treatment-related mortality	6 in the first 16 patients 7 in the first 20 patients 8 in the first 25 patients 9 in the first 29 patients 10 at any point	0.4	0.93
-----------------------------	---	-----	------

In addition to the primary endpoint, there are a number of secondary and correlative objectives.

Secondary Objectives:

1. Kaplan-Meier methodology will be used to compare overall survival.
2. The safety will be described by tabulating the number of transfusions, frequencies of bleeding and serious infections, and the use of G-CSF support.
3. We will also evaluate the following metrics: graft function; myeloid and T-cell chimerism; and acute and chronic GVHD incidence. Graft function will be examined after enrollment by summary statistics of hemoglobin levels, neutrophils and platelets. Myeloid and T-cell chimerism will be summarized as a continuous measurement at enrollment, 6, 9,12,18 months post-transplant and 24 months post-transplant. Cumulative incidence function will be used to estimate grade II-IV acute GVHD and chronic GVHD incidence.

Correlative Studies:

1. The global DNA methylation status will be evaluated at baseline, and the change from baseline will be explored among individuals who do and do not relapse by the 24 month BM evaluation. This continuous measurement will be compared using a rank-sum test.
2. The reoccurrence of cytogenetic abnormalities will be evaluated in the CD34 subpopulation of cells at the time of trial enrollment. This exploratory measure is calculated as the proportion of involved cytogenetic cells out of the total number of stem cells and may be a marker of disease burden following transplant. This proportion will be categorized and relapse will be contrasted across these categories using a permutation-based logrank test.
3. The composition of myeloid progenitor cells will be compared pre- and post- 5'-azacitidine treatment to explore whether normalization occurs following treatment. These paired measurements will be compared using McNemar's test.
4. The levels of regulatory T-cells and CD8+ will be graphically displayed across baseline and post-treatment time points.

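### Exactly 8 relapses in 32 patients has no verdict, and accrual closes one two-year relapse after success has become impossible

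*Combined protocol and SAP*

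**What the plan says.** Everything on this point is in section 14.1 (Biostatistics) of the combined protocol and SAP. The design is single-stage and exact, with 32 patients.

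- **Design rates.** On the favourable side, "this intervention would be considered promising if the two-year relapse proportion is 15% or less". On the other side: "If the relapse proportion is 35% or greater, the 5-azacitidine intervention would not be considered promising". The 35% is the institution's historical two-year cumulative incidence in patients who meet the entry criteria.
- **Success sentence**, applied at the end of the trial: "if seven or fewer patients relapse by two years post treatment initiation, the trial will be considered promising".
- **Failure and closure sentence**, which follows directly: "If, however, more than 8 patients relapse at any point the study will be considered unpromising and will be closed for further accrual".
- **Operating characteristics:** "The type I and type II errors for this trial are 0.08 and 0.10, respectively".
- **Accrual:** "It is anticipated that enrollment will be completed in 5 years with an accrual of approximately 6-7 patients/year".

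The safety stopping table in the same section also speaks of any point. Its treatment-related mortality row, for example, ends with "9 in the first 29 patients 10 at any point". There the number printed is the count that triggers stopping.

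**The concern.** In a single-stage design with one cut-off, the success and failure regions should be complementary. Here success is 7 or fewer and failure is 9 or more. The count of 8 belongs to neither, and it is the first count beyond the success limit, where the pressure to reinterpret a result is greatest.

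The trial has a single arm and a historical comparator, so its conclusion depends on a verdict fixed in advance. If 8 were called promising once the data were known, the type I error would be about twice the stated value.

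There are two further consequences:

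- **Late closure.** Once eight patients have relapsed within two years, 7 or fewer cannot be reached, yet accrual continues until a ninth relapse. Any patient enrolled in between joins a trial that cannot succeed.
- **Different windows.** Success counts relapses up to two years after treatment starts; closure counts them at any point. Taken literally, 7 relapses within two years plus 2 later ones would make the trial both promising and unpromising.

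**Working it through.** **Inputs, all from section 14.1:** n = 32; null relapse rate 0.35; target rate 0.15; success if X ≤ 7; failure if X ≥ 9. X is the number of relapses, taken as binomial(32, p).

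**1. Reproduce the plan's errors.**
- Type I error = P(X ≤ 7 | p = 0.35) = 0.0818, stated as 0.08.
- Type II error = P(X ≥ 8 | p = 0.15) = 1 − 0.9042 = 0.0958, stated as 0.10.

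Both agree at two decimals. The type II calculation counts 8 as a failure.

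**2. Try the other cut.** If 8 counted as promising:
- Type I error = P(X ≤ 8 | 0.35) = 0.0818 + 0.0766 = 0.1584.
- Type II error = P(X ≥ 9 | 0.15) = 0.0413.

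Neither matches the plan. The stated errors belong only to a rule in which 8 fails.

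**3. Size of the gap.** P(X = 8) = C(32, 8) p⁸ (1 − p)²⁴.

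| True relapse rate | P(X ≤ 7) promising | P(X = 8) no verdict | P(X ≥ 9) unpromising |
|---|---|---|---|
| 0.15 | 0.9042 | 0.0545 | 0.0413 |
| 0.20 | 0.6982 | 0.1272 | 0.1746 |
| 0.25 | 0.4325 | 0.1610 | 0.4065 |
| 0.30 | 0.2118 | 0.1322 | 0.6560 |
| 0.35 | 0.0818 | 0.0766 | 0.8416 |

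The two written verdicts together cover 0.9042 + 0.0413 = 0.9455 at 15%, and 0.0818 + 0.8416 = 0.9234 at 35%. The gap is widest at 25%, since P(X = 8) peaks at p = 8/32.

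**4. Do the design rates settle the matter?** No. 8/32 = 25%, which lies between 15% or less and 35% or more.

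**5. Cost of closing one relapse late, prompt detection.** Let T_r be the enrolment number of the patient who supplies the r-th relapse, with enrolment capped at 32. Then E[min(T_r, 32)] is the sum over k = 0 to 31 of P(Bin(k, p) ≤ r − 1).
- p = 0.35: 24.87 for the ninth relapse − 22.47 for the eighth = 2.40 patients.
- p = 0.25: 1.63 patients.
- p = 0.15: 0.28 patients.

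**6. The same cost with delayed relapse.** The protocol gives no distribution of relapse times, so two were assumed: uniform over two years, and front-loaded with 75% in the first year. Accrual was simulated as Poisson at 6, 6.5 and 7 patients per year, with p = 0.35.
- Uniform: mean 1.65, 1.59 and 1.51 extra patients.
- Front-loaded: mean 1.96, 1.90 and 1.86.
- No extra patient at all in about 40% to 52% of trials.

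**7. Windows.** At 6 to 7 patients per year, 32 patients take about 4.6 to 5.3 years (32/7 to 32/6). Early patients therefore pass their two-year mark while accrual is open, and a later relapse in one of them could count towards closure but not towards the success count.

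**The case against.** The best defence is that the plan already settles 8 by implication. It offers one route to a promising verdict, 7 or fewer, and 8 does not take it. The stated errors hold only if 8 fails. On this view a label is missing, not a decision boundary. Much of this stands: a careful reader would call 8 not promising. But the plan does not leave failure as the default. It writes its own threshold for unpromising, and 8 does not reach it, so someone could call 8 an intermediate result.

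A second defence is that the failure sentence is only an early-closure rule, which need not be the complement of the final success rule. Closing at 9 instead of 8 does leave both error rates unchanged, because 9 relapses within two years can never become 7. But the same sentence also declares the trial unpromising, so it carries a verdict. Even as a pure closure rule it acts one two-year relapse too late.

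Third, the accrual cost is small. This is fair. The 2.4 figure requires each relapse to be known before the next enrolment, and the delayed figures rest on assumed relapse times.

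Fourth, a result that is both promising and unpromising is unlikely. Section 4.3 says most relapses fall in the first year after transplant. Scheduled marrow assessments end 24 months after transplant, roughly 20 to 22 months after a start at day 60 to 120, and any point may simply mean any time during accrual, as in the safety table. That also stands. The window mismatch is a secondary wording fault, and no probability is attached to it here.

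**Conclusion.** The concern holds. The success rule, the sample size and the stated errors are sound; the failure and closure threshold is one too high. The main consequence is that 8 of 32 has no prespecified verdict. That result has probability 5.5% and 7.7% at the two design rates, and about one in six at a true rate of 25%. Calling it promising after the fact would raise the type I error from 0.082 to 0.158.

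The late closure is real but modest: a mean of about 1.5 to 2.4 patients at a 35% relapse rate, depending on how quickly relapses appear, and 0.3 or fewer at 15%. The statement that success is impossible after the eighth relapse applies to relapses within two years of treatment initiation.

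The probabilities assume 32 independent patients with known two-year relapse status and a common relapse rate. The delayed-accrual figures also depend on the assumed relapse-time distributions. The gap at 8 depends on none of these assumptions. Because this is the only efficacy rule in the trial, it should be corrected before it is applied.

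**What to change.** In section 14.1, reword the failure sentence so that the study is considered unpromising, and closed to further accrual, as soon as *8 or more patients relapse within two years of treatment initiation*. Leave the success sentence as it is.

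Every count is then classified (7 or fewer against 8 or more), both sentences use the same window, and accrual closes when success is no longer possible. The stated 0.08 and 0.10 then describe the whole rule. Closing the gap the other way, by counting 8 as promising, would contradict those errors (0.158 and 0.041).

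The cost is one sentence. No patients, data collection or analyses are added, and the sample size and stated errors stay the same.

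### The success rule counts relapses within two years, but the unpromising rule states no time window, so read literally the same data can give both verdicts

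*Combined protocol and SAP*

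**What the plan says.** Section 14.1 (Biostatistics) starts from a historical two-year figure: "cumulative incidence of relapse is 35"%. It sets the target on the same horizon: "this intervention would be considered promising if the two-year relapse proportion is 15% or less". The design is described as follows: "using a single stage exact design, a total of 32 patients will accrue on study".

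Two decision sentences follow.

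- Success: "At the end of the trial, if seven or fewer patients relapse by two years post treatment initiation, the trial will be considered promising".
- Failure and closure: "If, however, more than 8 patients relapse at any point the study will be considered unpromising and will be closed for further accrual".

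The first has a two-year window counted from treatment initiation. The second has none. The section gives type I and type II errors of 0.08 and 0.10, does not say which sentence prevails if both are satisfied, and adds: "It is anticipated that enrollment will be completed in 5 years". The protocol summary (section 1.0) defines the primary endpoint as the relapse rate after treatment initiation, also without a window.

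**The concern.** With five years of accrual, the first patients pass their two-year mark while later ones are still enrolling, and they may be observed for several years after it. A patient who relapses in year three is a non-relapse for the success rule. Taken at its word, the second rule counts that patient. A trial that ends with seven relapses by two years and two more afterwards has then satisfied both sentences.

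This is the primary decision rule of a single-arm trial that is judged on one count. Which relapses enter that count should be settled before the data are seen. If late relapses enter the unpromising count, the stated error rates no longer describe the rule being applied.

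**Working it through.** **Inputs from section 14.1.** n = 32; unpromising relapse proportion 0.35; target 0.15; promising if X ≤ 7, where X is the number of relapses within two years; unpromising if more than 8, that is 9 or more, with no window; accrual over 5 years.

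**Step 1: reproduce the plan's errors.** With X ~ Binomial(32, p):

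- Type I = P(X ≤ 7 | 0.35) = 0.082 (stated 0.08).
- Type II = P(X ≥ 8 | 0.15) = 0.096 (stated 0.10), so power is 0.904.

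Neighbouring cut-offs do not fit: X ≤ 6 gives 0.036 and 0.195; X ≤ 8 gives 0.158 and 0.041. The stated errors therefore belong to the two-year rule with seven or fewer as success and eight or more as failure.

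**Step 2: the monitoring reading.** If the second sentence means that the two-year count is watched throughout the trial, both rules use X. X cannot be both ≤ 7 and ≥ 9, so the probability of two verdicts is zero.

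**Step 3: the literal reading.** Let L be relapses after two years among the 32 − X patients relapse-free at two years. Both verdicts apply when X ≤ 7 and X + L ≥ 9.

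Assumptions not in the documents: entry time t uniform over 0 to 5 years, observation to year 7, constant hazard h after two years, no competing deaths, and all late relapses detected. A patient entering at t has 5 − t years at late risk, so the average late relapse probability is

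q = 1 − (1 − e^(−5h)) / (5h) = 0.025, 0.048, 0.071 for h = 0.01, 0.02, 0.03.

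Then P(both) = Σ over x = 0 to 7 of P(X = x) · P(Binomial(32 − x, q) ≥ 9 − x). If the unpromising rule governs, P(promising) = P(X ≤ 7) − P(both).

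| h per year | P(both), p = 0.15 | Type II, unpromising rule governs | P(both), p = 0.35 | Type I, unpromising rule governs |
|---|---|---|---|---|
| 0.01 | 0.017 | 0.113 | 0.006 | 0.076 |
| 0.02 | 0.063 | 0.159 | 0.019 | 0.063 |
| 0.03 | 0.131 | 0.227 | 0.032 | 0.049 |

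For example, at h = 0.02 type II is 1 − (0.904 − 0.063) = 0.159. Setting q directly to 2%, 5% or 10% gives P(both) = 0.011, 0.067 or 0.239 at the 15% target.

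**Step 4: closure during accrual.** This was simulated at the 15% target with the same entry pattern and late hazards, and a constant hazard in the first two years. The event is that nine relapses of any timing occur before the last patient enters, while the final two-year count is 7 or fewer. Its probability is about 0.03% to 0.04% at h = 0.01, under 0.2% at h = 0.02 and about 0.4% at h = 0.03. Nearly all the conflict in step 3 therefore arises after accrual has ended.

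**Step 5: exactly eight.** Even with both rules limited to two years, keeping the more-than-eight threshold leaves X = 8 without a verdict. P(X = 8) = 0.055 at 15% and 0.077 at 35%. Step 1 shows that the stated errors need eight to be unpromising.

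**The case against.** The strongest reply is that the phrase *at any point* is monitoring language. The safety table in the same section ends its stepped boundaries with it, after steps defined by the first so many patients, where it means whenever in the trial the count is reached. The relapse sentence also ends by closing accrual, and the sentences before it fix the endpoint at two years. This stands as a reasonable reading. It does not exclude the other: the relapse sentence has no stepped list before it, and the summary's endpoint has no window.

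A reader might infer that the two sentences flatly contradict each other, or that late relapses can shut down a trial that has already succeeded. The documents do not support either. The first inference needs the literal reading, which is open but not established. The second fails because success is judged only at the end of the trial, after accrual, and step 4 shows that early closure with a low two-year count is rare.

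The size also rests on outside inputs. Section 4.3 says most relapses occur in the first year after transplant, which favours the low end of the range. Scheduled marrows stop at 24 months after transplant (sections 9.1 and 10.0). Late relapses would have to surface clinically, as section 12.1 allows through circulating blasts or extramedullary disease. Finally, late counting is not harmful in one direction only: it costs power but lowers type I error.

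**Conclusion.** The point holds as an ambiguity in the primary decision rule. One reading gives no conflict. The literal reading lets a trial be promising and unpromising at once, with no rule for which prevails. Under the assumed late hazard of 1% to 3% per year and observation to year seven, that happens in about 2% to 13% of trials at the 15% target. Type II error would then be about 0.11 to 0.23, against the stated 0.10, and type I error about 0.08 to 0.05, against 0.082 for the two-year rule. These figures illustrate the size and are not estimates, because the documents give neither a late relapse risk nor a length of follow-up. What is at stake is chiefly the final label, not accrual. That the stated errors fit only the two-year rule with a cut-off of seven needs no assumption beyond the plan's own figures.

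**What to change.** Reword the two decision sentences in section 14.1 so that:

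- both rules count only relapses within two years of treatment initiation;
- seven or fewer such relapses is promising and eight or more is unpromising;
- accrual closes whenever in the trial the eighth such relapse is reached;
- relapses after two years are listed separately and do not enter either count.

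Adding the two-year window while keeping the more-than-eight threshold would not be enough, because exactly eight would still have no verdict. Closing at eight does not alter the errors, since success is already impossible at that count; they remain 0.082 and 0.096, matching the stated 0.08 and 0.10. The change is a short text edit and costs no patients or data.

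### Relapse has only a total-count closure rule; a staged relapse boundary would close accrual sooner under the null and still keep the stated 0.08 and 0.10 errors

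*Combined protocol and SAP*

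**What the plan says.** Section 14.1 takes a historical two-year "cumulative incidence of relapse is 35" percent as the unpromising level, and "this intervention would be considered promising if the two-year relapse proportion is 15% or less". The sample size follows: "using a single stage exact design, a total of 32 patients will accrue on study". The success rule is that "if seven or fewer patients relapse by two years post treatment initiation, the trial will be considered promising". The closure rule for relapse is "If, however, more than 8 patients relapse at any point the study will be considered unpromising and will be closed for further accrual", so accrual stops at the ninth relapse. On errors: "The type I and type II errors for this trial are 0.08 and 0.10, respectively".

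The early-termination table in the same section covers three safety events. Neutropenia and thrombocytopenia start at "3 in the first 8 patients" and end at 7 at any point. Treatment-related mortality starts at 3 in the first 5 and ends at 10 at any point. Relapse has no row, and no operating characteristics are given for its closure rule.

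**The concern.** The plan already means to close accrual when relapse looks too frequent, but its only trigger is a number that takes most of the cohort to reach at the null rate. Nine relapses at 35% correspond to about 9 / 0.35 = 25.7 patients with known outcome, and patients keep entering while relapses emerge. A run such as 6 relapses in the first 13 does not close accrual, although success would then need at most 1 relapse in the next 19.

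At stake is how many patients start a regimen whose main expected side effect is myelosuppression (section 7.0) after the data have turned against the hypothesis. The format needed to act sooner is already in use in the same section and requires no accrual pause.

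**Working it through.** **Inputs.** From section 14.1: N = 32; p0 = 0.35; p1 = 0.15; success if 7 or fewer relapse; closure at the ninth relapse; "with an accrual of approximately 6-7 patients/year". Section 4.3 says only that most relapses fall in the first year after transplant. Any relapse-time distribution is therefore an assumption.

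**1. The plan's own errors.** With X binomial(32, p):
- Type I = P(X ≤ 7 | 0.35) = 0.0818 (stated 0.08).
- Type II = P(X ≥ 8 | 0.15) = 0.0958 (stated 0.10).

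Both reproduce. Counting 8 relapses as success would give P(X ≤ 8 | 0.35) = 0.158, so the stated 0.08 requires 8 relapses to be a failure.

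**2. Method for boundaries.** Let f_n(x) be the probability of x relapses in the first n patients with no crossing so far:

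f_n(x) = (1 − p) f_{n−1}(x) + p f_{n−1}(x − 1).

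All mass at x ≥ k(n) is removed as the stopping probability s_n. Mean enrolment is Σ n·s_n + 32(1 − Σ s_n). Applied to the plan's table, this gives 0.098 and 0.924 for neutropenia and thrombocytopenia (stated 0.1 and 0.92), and 0.074 and 0.931 for mortality (stated 0.07 and 0.93).

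**3. Relapse rules compared.** The staged rule has k(n) = 5 for n ≤ 8, 6 for n ≤ 13, 7 for n ≤ 20 and 8 for n ≤ 32.

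| Rule | Type I | Type II | Mean enrolled at 35%, relapse known at once | With lag* |
|---|---|---|---|---|
| Plan: close at 9th | 0.0818 | 0.0958 | 24.9 | 28.2 |
| Close at 8th | 0.0818 | 0.0958 | 22.5 | 26.4 |
| Staged: 5/8, 6/13, 7/20, 8 | 0.0803 | 0.0995 | 19.6 | 24.1 |

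*Assumed: random entry at 6.4 per year, 70% of relapses in year 1 of 2, relapses among the first n counted whenever they occur.

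Under the plan's rule with immediate knowledge, the median is 25 and accrual closes before patient 32 in 81% of null trials. With even entry at 6 to 7 per year and three assumed relapse patterns (75% within six months, 75% within one year, uniform over two years), the plan's mean ranges from 26.8 to 29.3.

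**4. Splitting the saving.**
- Immediate knowledge: 24.9 − 22.5 = 2.4 from closing at the eighth relapse; 22.5 − 19.6 = 2.9 from the staging.
- With the lag in the table: 28.2 − 26.4 = 1.8, then 26.4 − 24.1 = 2.3.
- At 6.5 per year with 75% of relapses in year 1, the staging takes 25.8 to 23.3. If thresholds are read against current enrolment instead, it takes 25.8 only to 24.4.
- A similar boundary (4/5, 5/9, 6/13, 7/19, 8 at any point; type II 0.0999), simulated separately at the same rate and first-year share, takes 26.2 to 25.2.

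The staged part is thus worth roughly 1 to 3 patients.

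**5. Cost.** Power goes from 0.9042 to 0.9005, a loss of 0.0037. The probability of crossing is 0.0995 at 15% and 0.92 at 35%. Under the table's lag assumptions, accrual closes before 32 at the 15% target in 4.6% of trials, against 1.2% now and 3.7% with closure at the eighth alone. All of these closures lie within the 0.0995.

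**6. Tighter boundaries.** Using the mortality table's early limits (3/5, 4/8, 5/12, 6/16, 7/20, then 8 at any point) gives type II 0.124, above the stated 0.10.

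**The case against.** The plan declares a single-stage design, its errors reproduce, and nothing in it promises an interim look at relapse. The staged table is there to limit risk and confirm safety, which is a different purpose from futility, and it already guards against myelosuppression. Accrual does close for relapse, at the ninth. All of this stands, and it is why the point is an improvement and not a defect. It does not remove the point, because the plan itself wants early closure for lack of effect and could have it sooner at almost no cost.

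Three stronger readings are tempting but unsupported:
- **An inactive drug goes to nearly the whole cohort.** The exact figure is 24.9 of 32, or 78%. Values of 27 to 29 need a lag distribution that the documents do not give.
- **After 6 relapses in 13, success is out of reach.** The chance of at most 1 in the next 19 is 0.003 at 35% but 0.20 at 15%. For 5 in 8 it is 0.28 at 15%, and for 7 in 20 it is 0.14. Stopping there is a trade-off.
- **Any early boundary keeps the errors.** Only selected ones do, as the 0.124 shows.

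It is also fair that the errors assume 32 patients evaluable for relapse. Section 13.0 counts some patients for toxicity only and replaces others, so the first n must be defined.

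**Conclusion.** The point holds as an optional, low-cost improvement. Relapse has no early futility boundary, and one exists that keeps both stated errors at N = 32 (0.080 and 0.0995). At 35% relapse it lowers mean enrolment from 24.9 to 19.6 if relapses are known at once, or from about 28 to about 24 under the tabulated lag. Much of that gain is available simply by closing at the eighth relapse, which costs nothing because eight relapses already rule out seven or fewer.

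The error figures are exact for 32 evaluable patients and treat any crossing as an unpromising result. The lagged enrolment figures rest on assumed accrual and relapse-time patterns and are indicative only.

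**What to change.** Add a relapse row to the early-termination table in section 14.1: close accrual at 5 relapses in the first 8 evaluable patients, 6 in the first 13, 7 in the first 20, or 8 at any point, counting relapses within two years of treatment initiation. Report the probability of crossing as 0.0995 at 0.15 and 0.92 at 0.35. Keep success at 7 or fewer of 32, and state that a crossed boundary means unpromising.

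Define the first n by order of entry among patients evaluable for the primary endpoint, consistent with section 13.0, and say how the order is renumbered when a patient is replaced. The row governs accrual only and leaves the care of enrolled patients unchanged.

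The cost is this text, about 0.4 percentage points of power, and fewer patients for secondary and correlative analyses if accrual closes early. If the staging is not wanted, closing at the eighth relapse alone leaves both errors unchanged and lowers mean enrolment at 35% from 24.9 to 22.5 with immediate knowledge.

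### Replacing patients lost to follow-up makes membership of the 32 depend partly on outcome, so the relapse count does not estimate the two-year cumulative incidence behind the 35% benchmark

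*Combined protocol and SAP*

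**What the plan says.** Section 14.1 takes its benchmark from historical data at the centre: the two-year "cumulative incidence of relapse is 35" per cent. The target is that "this intervention would be considered promising if the two-year relapse proportion is 15% or less". The design is fixed as follows: "using a single stage exact design, a total of 32 patients will accrue on study". The decision rule is a raw count: "if seven or fewer patients relapse by two years post treatment initiation, the trial will be considered promising". The error statement is "The type I and type II errors for this trial are 0.08 and 0.10, respectively".

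The same section then says who belongs to the 32:

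- **Ineligible patients.** The condition for replacement reads "If a patient is found to be ineligible for reasons unrelated to disease relapse or progression".
- **Lost patients.** The sentence continues "or is lost to follow-up, s/he will be replaced for the primary endpoint". The restriction to reasons unrelated to relapse is attached to ineligibility and, as written, does not reach loss. No time limit is given.
- **Deaths without relapse.** For such a patient, "s/he will remain as part of the 32 patient cohort".

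Section 13.0 adds that relapse before four cycles is evaluable. It also says that patients off study before four cycles for reasons other than toxicity are replaced. Section 14.1 plans a cumulative incidence function for GvHD only. The documents contain no censored analysis of relapse, no sensitivity analysis for replaced patients and no expected loss rate.

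**The concern.** A patient who relapses at month 3 and then stops attending is counted as a relapse. A patient who stops attending at month 3 without relapse is removed, and someone else takes the place. Whether a patient with interrupted follow-up belongs to the 32 thus depends on whether relapse came first.

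A cumulative incidence, which is what the 35% is, keeps a lost patient at risk until censoring. The replacement rule discards that relapse-free time, so the trial's proportion and its benchmark are different quantities. If loss is unrelated to relapse, the retained proportion is too high and the test is harder to pass. If patients tend to be lost because they are deteriorating, likely relapses are removed and the test is easier to pass. Replacement also removes the information needed to tell which has happened.

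Late loss is plausible. Treatment starts 60 to 120 days (about 2 to 4 months) after transplant, so the endpoint falls at about 24 + 2 = 26 to 24 + 4 = 28 months after transplant. The last scheduled marrow in Sections 9.1 and 10.0 is at 24 months after transplant.

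**Working it through.** **Step 1: the plan's own figures.** Inputs from Section 14.1: n = 32, promising if X ≤ 7, relapse 35% (null) and 15% (target). Exact binomial:

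- Type I error = P(X ≤ 7 | 32, 0.35) = 0.0818.
- Type II error = P(X ≥ 8 | 32, 0.15) = 0.0958, so power is 0.904.

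Both agree with the stated 0.08 and 0.10. They hold if the 32 counted patients relapse at the true rate.

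**Step 2: loss independent of relapse (loss rates assumed).** Take constant relapse and loss hazards over two years and no competing death. Let p be the true two-year relapse incidence and L the two-year loss probability in the absence of relapse.

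- P(relapse seen) = ln(1−p) / [ln(1−p) + ln(1−L)] × [1 − (1−p)(1−L)]
- P(lost first) = ln(1−L) / [ln(1−p) + ln(1−L)] × [1 − (1−p)(1−L)]
- Retained proportion q = P(relapse seen) / [1 − P(lost first)]

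For p = 0.15 and L = 0.10, 1 − 0.85 × 0.90 = 0.235 and the relapse share is 0.1625/0.2679 = 0.607. Relapse seen is therefore 0.1426, lost first is 0.0924, and q = 0.1426/0.9076 = 0.157. Entering q in the rule of Step 1:

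| Assumed loss | True 15% appears as | Power | True 35% appears as | Type I error |
|---|---|---|---|---|
| 0 | 15.0% | 0.904 | 35.0% | 0.082 |
| 5% | 15.3% | 0.894 | 35.6% | 0.071 |
| 10% | 15.7% | 0.882 | 36.3% | 0.061 |
| 20% | 16.5% | 0.853 | 37.8% | 0.043 |

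Adding an assumed 15% of deaths without relapse at 10% loss gives 15.6% and 36.0%, with power 0.886 and type I error 0.065. If 80% of relapses fall in the first year, 20% loss gives power 0.836 and type I error 0.037.

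**Step 3: loss linked to relapse (assumed).** Let a share L of enrolled patients be lost, 60% of whom would have relapsed, with a true overall rate of 35%. Then q = (0.35 − 0.60 L)/(1 − L).

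| L | q | Type I error |
|---|---|---|
| 5% | 0.32/0.95 = 0.337 | 0.108 |
| 10% | 0.29/0.90 = 0.322 | 0.143 |
| 15% | 0.26/0.85 = 0.306 | 0.192 |

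The 60% has no source in the documents. At 10% loss, 50% or 70% in its place gives 0.115 or 0.175.

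**Step 4: what replacement hides.** Suppose 7 of the 32 retained patients relapse and 4 others were replaced. The reported figure is 7/32 = 21.9%. Among the 36 treated, the true proportion lies between 7/36 = 19.4% and 11/36 = 30.6%.

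**Step 5: where the cut-off must sit if losses are censored.** With a limit of exactly 7/32 = 21.9%, seven relapses and one early loss give about 7/31 = 22.6%, a failure. The limit has in effect become six: P(X ≤ 6 | 31, 0.15) = 0.827. In simulation (constant hazards, 10% independent loss, no competing death) power is about 0.84, below the 0.882 under replacement. With a limit of 7.5/32 = 23.4%, 7/31 passes, and the simulated power is about 0.88 to 0.91 with type I error about 0.10 at 5% to 20% loss.

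**The case against.** Several points for the plan stand.

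- **Size.** No loss rate is given. This is a single-centre transplant cohort with scheduled marrow examinations to 24 months, and loss may be small. At 5% independent loss the effect is slight and conservative for type I error. A reader might infer that the stated error rates are wrong; the documents do not support that. They are correct for the rule as written and shift only if loss is material.
- **Timing.** A reader might infer that the plan expressly replaces patients lost as late as month 20. Section 14.1 only omits a limit, and Section 13.0 restricts its own off-study replacement to before four cycles. Late replacement is one reading. The primary-endpoint sentence carries no such restriction, however, so the gap remains.
- **Composition.** It is tempting to say that the 32 consist only of relapsers and of patients followed relapse-free for two years. That is not so, because deaths without relapse are kept. Keeping them agrees with a competing-risk cumulative incidence and is not a fault.
- **Remedy.** Censoring assumes non-informative loss and does not correct the direction that favours the drug. In the Step 3 scenario, with relapse times assumed uniform, censoring with a 21.9% limit gives simulated type I error of about 0.136 at 10% loss and 0.206 at 15%, against 0.143 and 0.192 under replacement. A higher limit can only pass more trials, so inflation at 23.4% is no smaller than this. The bounds in all treated patients are therefore an essential part of the change.

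**Conclusion.** The concern holds in a conditional form. Section 14.1 makes membership of the 32 depend partly on outcome, and the resulting proportion does not estimate the quantity behind the 35% benchmark. Nothing elsewhere in the documents repairs this.

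The effect is nil without loss. Under independent loss of 5% to 20% it is a shift of about 0.3 to 1.5 percentage points at a true 15%, with power falling to between 0.894 and 0.853 and type I error also falling. Under the assumed relapse-linked loss of 5% to 15%, type I error rises to between 0.108 and 0.192. All loss rates, and the relapse risk among those lost, are assumptions.

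A reader might infer that the rule favours the drug. The documents do not support a direction: it depends on why patients are lost, which replacement leaves unexamined.

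**What to change.** 1. Delete the loss-to-follow-up clause from the replacement sentence in Section 14.1, and reconcile the result with the off-study replacement rule in Section 13.0. If that rule is left as it is, patients off study before four cycles would still be replaced.
2. Keep all treated patients. Estimate the two-year cumulative incidence of relapse from treatment start, with death as a competing event and losses censored at the last disease assessment. Reconcile the two-year horizon with the last scheduled assessment, which at present falls before it.
3. Set the cut-off between 7/32 and 8/32, for example promising if the estimate is below 7.5/32 = 23.4%. It should not be exactly 21.9%. With no loss the estimate is a multiple of 1/32, so seven relapses pass and eight (25.0%) do not, as in the present rule. One censored patient no longer turns seven relapses into a failure by itself.
4. Report bounds over all treated patients: lost patients counted as not relapsed (best case) and as relapsed (worst case). State the number lost, with timing and reason.

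The cost is wording plus a method already planned for GvHD, and no replacements for loss are needed at an accrual of 6 to 7 patients a year. The downside is that, with losses, the error rates are approximate rather than exact: simulated type I error is about 0.10 and power about 0.88 to 0.91 at 5% to 20% independent loss, without competing death. Relapse-linked loss can still inflate type I error in the primary estimate, so a promising result should be read together with the worst-case bound.
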